3.2.2 Secondary Efficacy Analyses

All secondary efficacy endpoints will be analyzed using the mITT analysis set.

All secondary efficacy endpoints (see section 1.2.2) will be summarized descriptively by treatment group. The continuous variables will be summarized descriptively using number of subjects (missing), mean, standard deviation, median, quartile, minimum and maximum. Categorical data will be summarized descriptively by frequencies along with the associated percentages. No inferential statistics will be generated for the secondary efficacy endpoints.

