████████ have a unique barbed design, which, theoretically, allows physicians to perform highly efficient continuous suture, and to improve operation efficiency. By reducing the operation time, the new product can achieve the same safety and effectiveness as compared with the interrupted suture technique [5, 7-10].

This study was designed to verify that ██████████ can improve the operation efficacy, can reduce the suturing and operation time as well as meet the clinical demand for suture safety, as compared to traditional interrupted suture technique during TKA surgery.

[figure not shown]

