## 2.0 Study Objectives

The primary objective of this prospective, randomized controlled study is to evaluate the wound closure efficiency of [REDACTED] compared to conventional sutures in patients undergoing TKA. For the purpose of this study, wound closure efficiency is defined as the total time required to close the surgical incisions in patients undergoing TKA procedures using [REDACTED] compared to those using traditional sutures. Secondary objectives will include the evaluation of differences in overall surgical procedure time, operation room (OR) time, length of stay, procedure costs, quality of life measures including pain, and range of motion (ROM). In addition, the difference in the safety profiles for both wound closure procedures will be evaluated through the analysis of the incidence of wound complications including dehiscence, wound infections, and other adverse events.

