1.1.2 Secondary Objective(s)

Secondary objectives will include the evaluation of differences in overall surgical procedure time, operation room (OR) time, length of stay, procedure costs, quality of life measures including pain, and range of motion (ROM).

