1.2.2 Secondary Efficacy Endpoint(s)

Secondary efficacy endpoints include:

1. Duration of procedure (Total Operation Time): defined as the time in minutes elapsed from first incision to the skin closure;
2. Overall operating room (OR) time: defined as the time in minutes from the patient entering to exiting the OR;
3. Length of stay between surgery and discharge;

4. TKA related Quality of Life (QoL) assessments:

a. Knee Pain: pain at rest and pain during mobilization is measured using a 10 centimeter Visual Analogue Scale (VAS) in which patient is asked to describe degree of pain with 0 being no pain and 10 being the worst pain;

b. Health-related Quality of Life (EQ-5D-3L): patient is asked to confirm his/her health state by selecting the most appropriate level for each of the following 5 dimensions. Refer to Table 1.

- Mobility
- Self-care
- Usual activities
- Pain/discomfort
- Anxiety/depression

Table 1: EQ-5D-3L

By placing a tick in one box in each group below, please indicate which statements best describe your own health state today.

Mobility

I have no problems in walking about

I have moderate problems in wlaking about

I am unable to walk about

Self-care

I have no problems washing or dressing myself

I have moderate problems washing or dressing myself

I am unable to wash or dress myself

Usual Acitivities (i.e work, study, housework, family or leisure activities)

I have no problems doing my usual activities

I have moderate problems doing my usual activities

I am unable to do my usual activities

Pain/Discomfort:

I have no pain or discomfort

I have moderate pain or discomfort

I have extreme pain or discomfort

Anxiety/Depression

I am not anxious or depressed

[figure not shown]
I am moderate anxious or depressed

I am extremely anxious or depressed

To help people say how good or bad a health state is, we have drawn a scale (rather like a thermometer) on which the best state you can imagine is marked **100** and the worst state you can imagine is marked **0**.

We would like you to indicate on this scale how good or bad your own health is today, in your opinion. Please do this by drawing a line from the box below to whichever point on the scale indicates how good or bad your health state is today.

Your own
health state
today

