2.4 MULTIPLE COMPARISONS/MULTIPLICITY

All secondary endpoints and/or any further sensitivity or exploratory analyses for the primary and secondary endpoints will serve as supportive evidence only and therefore no adjustment for multiple comparisons will be performed.

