3.4 OTHER EXPLORATORY ANALYSIS

Not applicable.

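### Operation time is a stated target and a secondary objective about differences, but the plan prespecifies no between-arm comparison for it

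*SAP*

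**What the plan says.** Protocol 1.1 gives the purpose of the study as verifying that the device "can reduce the suturing and operation time as well as meet the clinical demand for suture safety". The same section links shorter operations to fewer incisional complications.

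Protocol 2.0 turns this into a formal objective: "Secondary objectives will include the evaluation of differences in overall surgical procedure time". SAP 1.1.2 repeats it: "Secondary objectives will include the evaluation of differences in overall surgical procedure time, operation room (OR) time, length of stay". The first secondary efficacy endpoint in SAP 1.2.2 is "Duration of procedure (Total Operation Time): defined as the time in minutes elapsed from first incision to the skin closure".

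The planned analysis is in SAP 3.2.2: "The continuous variables will be summarized descriptively using number of subjects (missing), mean, standard deviation, median, quartile, minimum and maximum", by treatment group in the mITT set, followed by "No inferential statistics will be generated for the secondary efficacy endpoints". Protocol 4.5.4 carries the same bar. SAP 2.4 says that secondary endpoints "will serve as supportive evidence only and therefore no adjustment for multiple comparisons will be performed". SAP 3.4, on other exploratory analysis, reads "Not applicable". The confidence interval and superiority rule in protocol 4.5.4 and SAP 3.2.1.1 apply to closure time only.

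**The concern.** An objective to evaluate differences needs an analysis that yields a difference. For operation time the plan yields two columns of per-arm statistics and nothing that compares them. The choice of comparison (estimator, interval, analysis set) is therefore left until after the results are known.

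Operation time also carries the protocol's argument for patient benefit. Closure time is the measured primary outcome, but section 1.1 reasons from shorter operations to fewer complications. If the report shows two means side by side, a gap between them may be taken as the promised verification, or a lack of one as failure, with no agreed statement of how precisely the gap was estimated.

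**Working it through.** **Step 1. Match objective to analysis.**

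| Element | Closure time | Duration of procedure |
|---|---|---|
| Named in the purpose (protocol 1.1) | yes | yes |
| Formal objective | primary | secondary, worded as differences |
| Per-arm summary | yes | yes |
| Between-arm difference | yes | none listed |
| Interval | one-sided 97.5% | barred |
| Decision rule | upper limit below 0 | none |

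No other section fills the right-hand column. SAP 2.4 sets the status of secondary endpoints without adding a comparison, and SAP 3.4 plans nothing.

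**Step 2. Reproduce the plan's own figures (closure time).** Inputs are 77 evaluable per arm, 90% power, one-sided 0.025, SD 8 and 16% withdrawal (protocol 4.5.2), and a control mean of 16.89 min (SAP 1.3.3).

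- Inflation: 77 / (1 − 0.16) = 91.67, rounded up to 92. This matches.
- The target difference is redacted, so it is back-solved. Normal approximation: 8 × √(2/77) × (1.960 + 1.282) = 4.18 min. Noncentral t: 4.21 min.
- A 25% reduction of 16.89 is 4.22 min, which returns 77 per arm by t-test (power 90.2%). The 25% is inferred, not read from the documents.

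The sample size is consistent with the visible inputs. It does not address operation time.

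**Step 3. What an interval for operation time would look like.** The documents give neither an SD nor an expected difference for operation time. Assume an SD of 10 to 30 min, and that the whole inferred closure saving of 4.22 min carries through.

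- SE = SD × √(2/n)
- 95% half-width = t × SE, with t = 1.976 (152 df, n = 77) or 1.973 (182 df, n = 92)
- Chance that the whole interval lies below zero: noncentral t, noncentrality 4.22/SE, one-sided 0.025

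| Assumed SD (min) | SE, n = 77 | Half-width | Chance | SE, n = 92 | Half-width | Chance |
|---|---|---|---|---|---|---|
| 10 | 1.61 | 3.18 | 74% | 1.47 | 2.91 | 81% |
| 15 | 2.42 | 4.78 | 41% | 2.21 | 4.36 | 48% |
| 20 | 3.22 | 6.37 | 26% | 2.95 | 5.82 | 30% |
| 30 | 4.83 | 9.55 | 14% | 4.42 | 8.73 | 16% |

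Both sample sizes are shown because 77 is the evaluable number the plan relies on and 92 is the number randomised. The mITT set also drops subjects not closed with the randomised suture.

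**Step 4. How far raw means can mislead.** Suppose there is no true difference and 92 per arm. The chance that the means favour the device by 2 min or more (an arbitrary threshold) is 1 − Φ(2/SE): 1 − Φ(2/1.47) = 8.7% at SD 10, 1 − Φ(2/2.95) = 24.9% at SD 20, and 1 − Φ(2/4.42) = 32.6% at SD 30.

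**The case against.** Descriptive-only secondary endpoints are a legitimate choice. The protocol and SAP agree on it, and SAP 2.4 declares these endpoints supportive. The hypotheses, sample size and superiority rule concern closure time alone, so there is no operation-time decision rule left unmet. The verification wording sits in a background section and could simply be softened. All of this stands. It does not remove the mismatch with the formal objective, which asks for differences in both documents.

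A reader might infer that the trial cannot support or refute a reduction in operation time, or that it will offer no measure of precision. The documents do not support that. SAP 3.2.2 requires n, mean and SD per arm, which are all the inputs for an unadjusted two-sample t interval. The primary analysis is of the same unadjusted kind, with no centre adjustment. What is missing is prespecification, not information.

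Closure time also lies inside operation time by definition, and protocol 3.4 says that the groups differ only in suturing material and technique. A demonstrated closure saving is thus a saving within the operation unless something offsets it. Unblinded surgeons make an offset possible, so this narrows the gap without closing it. The documents give no expected operation duration, so it cannot be said from them how large a share closure takes.

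A reader might also conclude that a formal test of operation time, gated on the primary, is needed. That goes too far. It would sit badly with the supportive status in SAP 2.4. At SD 20 to 30 it would usually miss a full 4.2 min saving: 90% power would need about 472 to 1061 per arm (normal approximation).

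**Conclusion.** The point holds as a mismatch between a stated objective and its analysis. Both documents promise an evaluation of differences in procedure time, protocol 1.1 speaks of verifying a reduction, and no prespecified between-arm comparison follows.

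It is a modest, inexpensive improvement. The primary conclusion is not affected, and nothing here challenges the sample size.

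The mismatch itself rests only on the text. The figures for precision and for the chance of detection rest on three assumptions: an operation-time SD of 10 to 30 min, a 4.2 min saving inferred from a redacted effect, and full carry-through to the whole operation. Within that range the half-width exceeds the inferred saving from SD 15 upward at either sample size. An interval would then be informative mainly by showing how uncertain the operation-time effect is.

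**What to change.** In SAP 3.2.2 and protocol 4.5.4, replace the blanket bar for this endpoint with the following:

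- Report the between-arm difference in mean Duration of procedure with a two-sided 95% confidence interval (t-distribution, mITT set), labelled supportive and without a confirmatory test.
- Do the same for Overall OR time once its two definitions are reconciled. Protocol 2.2 starts the clock at anesthesia; SAP 1.2.2 starts it when the patient enters the room.
- State that a reduction in operation time will not be described as verified unless the whole interval lies below zero. This limits the wording and does not turn a supportive endpoint into a confirmatory claim. Alternatively, reword the purpose statement in protocol 1.1.

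The cost is a short paragraph in each document, an entry in SAP section 5 (which now records no changes), and two rows in the table shells. No new data and no larger sample are needed, and SAP 2.4 can stay as written. The downside is that the interval may well include zero, in which case the operation-time wording would have to be softened.

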3.3 SAFETY ANALYSIS

Safety variables include the incidence of SSI, ASEPSIS score (only for subjects with confirmed SSI), AIRE score, incidence of wound separation or dehiscence requiring intervention, incidence of delayed wound healing events, incidence of AEs and SAEs associated with wound closure.

All safety endpoints (see section 1.2.3) will be summarized descriptively by treatment group for the Safety analysis set using available data. There will be no missing data imputation for the safety analysis. The continuous variables including ASEPSIS total score (ranging from 0 to 100), and AIRE total score (ranging from 0 to 12) calculated as the sum

of individual scores for Erythema, Oedema, Pain and Temperature, will be summarized descriptively by number of subjects, mean, standard deviation, minimum, and maximum. Categorical data including the incidence of SSI, incidence of wound separation or dehiscence requiring intervention, incidence of delayed wound healing events, incidence of AEs and SAEs associated with wound closure will be summarized descriptively by frequencies along with the associated percentages. No inferential statistics will be generated for the safety endpoints.

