- Report infection that involves both superficial and deep incision sites as deep incisional SSI;
- Report an organ/space SSI that drains through the incision as a deep incisional SSI.

3) Organ/Space SSI:

Infection occurs within 30 days after the operation if no implant is left in place or within 1 year if implant is in place and the infection appears to, be related to the operation and infection

involves any part of the anatomy (e.g., organs or spaces), other than the incision, which was opened or manipulated during an operation and at least one of the following:

- Purulent drainage from a drain that is placed through a stab wound into the organ/space;
- Organisms isolated from an aseptically obtained culture of fluid or tissue in the organ/space;
- An abscess or other evidence of infection involving the organ/space that is found on direct examination, during reoperation, or by histopathologic or radiologic examination;
- Diagnosis of an organ/space SSI by a surgeon or attending physician.

No confirmatory culture will be required unless deemed by the physician per local standard of care to provide appropriate treatment to subject.

b. ASEPSIS Score (only for patients with confirmed SSI): assesses severity of wound infection using numerical scoring (as opposed to the CDC's absence or presence of SSI and type). The ASEPSIS Wound Score evaluates wound characteristics and additional treatments as predictors of infection that may develop once the subject leaves the hospital. These include the presence of serous exudates, erythema, purulent exudates, separation of deep tissues, antibiotics, drainage of pus, wound debridement, isolation of bacteria, and requirement for inpatient stay. Surgeons assess each parameter and provide a numerical score based upon objective criteria of wound appearance and clinical consequences of the infection. Extra points were added for antibiotic treatment of SSI (10 points), drainage of pus under local anesthesia (5 points), debridement of the wound under general anesthesia (10 points), isolation of bacteria from the wound (10 points), and an inpatient stay of more than 14 days (5 points). An overall score, ranging from 0 to 100, is then calculated to define wound severity according to the proportion of the wound affected by each of these characteristics. Refer to Table 2:

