#### **4.5.2 Determination of Sample Size**

The proposed sample size of 92 patients per arm (184 total) is considered adequate to test the hypothesis that [REDACTED] can reduce the time for incision closure compared to conventional sutures. Based upon a review of the literature, the mean incision closure time was assumed to be [REDACTED] minutes for conventional sutures, being calculated as a weighted (based on number of subjects) mean of the means observed in the studies reviewed. The studies reported incision closure times ranging between 14.4 to 26.5 minutes [5, 7-10]. It is expected that the [REDACTED] can reduce the incision closure time by [REDACTED] % compared to conventional sutures; therefore, the assumed mean closure time for [REDACTED] is [REDACTED] minutes. The standard deviations observed in the reviewed literature range from 3.43 to 8.5 minutes for the conventional sutures; the standard deviation for this study was conservatively assumed to be [REDACTED] minutes in both groups for several

reasons, such as the lack of data for [REDACTED] and that this patient sample may be older and with larger BMI. The distribution of incision closure time is assumed to be normal.

The statistical hypotheses for the primary endpoint are as follows:

- H0: Mean Barbed  $\geq$  Mean conventional suture tested against the alternative hypothesis
- Ha: Mean Barbed  $<$  Mean conventional suture;

Where:

- The assumed mean time to incision closure in conventional group is [REDACTED] minutes;
- The mean time to closure in [REDACTED] is [REDACTED] minutes;
- The assumed standard deviations in the two groups are both 8.

Based upon these assumptions, a total seventy seven (77) evaluable subjects per arm will achieve 90% power to detect a difference of [REDACTED] minutes (expected mean for [REDACTED] of [REDACTED] minutes and the conventional group of [REDACTED] minutes) with estimated group standard deviations of [REDACTED] using a one-sided two-sample t-test. The assumed one-sided significance level is 0.025.

If the higher limit of the one-sided 97.5% confidence interval for the difference in the Mean [REDACTED] time minus the Mean closure time for conventional suture is smaller than 0, then it will be concluded that [REDACTED] is considered to be superior to conventional suture. The sample size is adjusted to 92 per arm to account for a 16% withdraw rate [25-28].

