1.3 SUMMARY OF THE STUDY DESIGN

1.3.1 General Study Design and Plan

This is a multicenter, single blind, prospective, randomized controlled study in patients undergoing elective TKA and meeting the study's eligibility criteria. Eligible patients will be randomized on 1:1 basis to have the surgical incision closed with either [REDACTED] or conventional sutures. Wound closure and surgical procedure times will be determined perioperatively. Patients will remain blinded to the type of sutures utilized for closure of the incision.

The schedule of events is depicted in Table 4 below.

Table 4: Schedule of Events

Event	Visit 1	Visit 2	Visit 3	Visit 4	Visit 5
	Baseline/ Screening ^a	Randomization	Procedure	Post-Op through Discharge ^b	30-42 days ^c (post procedure)
Informed consent	X				
IWRS/IVRS ^d		X			
Inclusion/Exclusion	X	X			
Urine/blood pregnancy test	X				
Demographics	X				
Medical/Surgical history	X		X		
Physical examination ^e	X			X	X

	Visit 1	Visit 2	Visit 3	Visit 4	Visit 5
Event	Baseline/ Screening ^a	Randomization	Procedure	Post-Op through Discharge ^b	30-42 days ^c (post procedure)
Knee pain VAS	X			X	X
EQ-5D-3L	X			X	X
Concomitant medications ^f	X	X	X	X	X
Length of stay ^g				X	
Health Economic				X	
Procedural data ^h			X		
Adverse events			X	X	X
Wound			X	X	X
SSI/ASEPSIS score ⁱ				X	X
AIRE score				X	X
Study completion					X

- a. To be performed within 30 days of surgery.
- b. Data will be collect on 3-5 days after surgery (expect for the length of stay and health economic data).
- c. Unless withdrawn from the study, subject's status will be confirmed at the time of in-person visit at 30-42 days following surgery. If possible, an in-person visit will be scheduled to confirm status for patients withdrawn prematurely from the study for any reason.
- d. Interactive web response system/ Interactive voice response system.
- e. The physical examination at baseline/screening visit includes height, weight and ROM of knee, and the post-procedure physical examination only includes ROM of knee.
- f. Including pain medications and antibiotics (except for anesthesia medications).
- g. Defined as time between procedure and discharge.
- h. Procedure time, overall OR time, intra-operative device failure rates, operating room resource utilization (if applicable), and anesthesia method (e.g., general or lumbar anesthesia).
- i. ASEPSIS score will be applied only after SSI confirmed.

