1.3.3 Sample Size and Statistical Power Considerations

The proposed sample size of 92 patients per arm (184 total) is considered adequate to test the hypothesis that [REDACTED] can reduce the time for incision closure compared to conventional sutures. Based upon a review of the literature, the mean incision closure time was assumed to be 16.89 minutes for conventional sutures, being calculated as a weighted (based on number of subjects) mean of the means observed in the studies reviewed. The studies reported incision closure times ranging between 14.4 to 26.5 minutes [4-8]. It is expected that the [REDACTED] can reduce the incision closure time by [REDACTED] compared to conventional sutures; therefore, the assumed mean closure time for [REDACTED] is [REDACTED] minutes. The standard deviations observed in the reviewed literature range from [REDACTED] to [REDACTED] minutes for the conventional sutures; the standard deviation for this study was conservatively assumed to be [REDACTED] minutes in both groups for several reasons, such as the lack of data for [REDACTED] and that this patient sample may be older and with larger Body Mass Index (BMI). The distribution of incision closure time is assumed to be normal.

The statistical hypotheses for the primary endpoint are as follows:

- H_0 : Mean Barbed \geq Mean conventional suture tested against the alternative hypothesis
- H_a : Mean Barbed $<$ Mean conventional suture;

Where:

- The assumed mean time to incision closure in conventional group is [REDACTED] minutes;
- The mean time to closure in [REDACTED] is [REDACTED] minutes;

- The assumed standard deviations in the two groups are both [REDACTED]

Based upon these assumptions, a total seventy-seven (77) evaluable subjects per arm will achieve 90% power to detect a difference of [REDACTED] minutes (expected mean for [REDACTED] of [REDACTED] minutes and the conventional group of [REDACTED] minutes) with estimated group standard deviations of [REDACTED] using a one-sided two-sample t-test. The assumed one-sided significance level is [REDACTED]

If the higher limit of the one-sided 97.5% confidence interval for the difference in the Mean [REDACTED] time minus the Mean closure time for conventional suture is smaller than 0, then it will be concluded that [REDACTED] is considered to be superior to conventional suture. The sample size is adjusted to 92 per arm to account for a 16% withdraw rate [9-12].

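### SAP 3.3 summarises ASEPSIS by arm as a mean and SD among confirmed-SSI subjects only, so the two means do not compare the randomised groups and can point opposite to the wound outcome

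*SAP*

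**What the plan says.** Both documents restrict the score to infected subjects. Protocol 2.3 defines it as "ASEPSIS Score (only for patients with confirmed SSI): assesses severity of wound infection using numerical scoring". Note i to the schedule of events in SAP 1.3.1 (Table 4) repeats this for data collection: "ASEPSIS score will be applied only after SSI confirmed".

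SAP 3.3 then lists the score among the continuous safety variables: "The continuous variables including ASEPSIS total score (ranging from 0 to 100". It is to be summarised by treatment group with number of subjects, mean, SD, minimum and maximum, on available data and without imputation. The same section reports SSI incidence by arm as frequencies and percentages on the Safety set (everyone who receives surgery, SAP 2.2), and rules out inferential statistics for safety endpoints.

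Table 2 in each document divides the total score into five severity categories. SAP 3.3 does not use them. The tables also differ: the protocol's third band is 21-30, while the SAP's is 20-30 and overlaps its own 11-20 band.

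**The concern.** A subject enters the ASEPSIS summary only by having an SSI. That is an outcome of treatment, and the trial's own rationale expects closure method to influence it: Protocol 1.1 links shorter operations to a lower risk of incisional complications, SSI in particular, and says the barbed suture is meant to shorten the operation. The two arms may therefore send different kinds of patient into the scored subgroup, and randomisation no longer makes the groups comparable.

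Entry also depends partly on judgement. The implanting surgeon cannot be blinded (Protocol 3.3.2), a diagnosis by the surgeon or attending physician is enough for an SSI, and culture is not required (Protocol 2.3). If mild infections were called more readily in one arm, that arm's mean would fall with no true difference in wounds.

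At stake is the reading of one listed safety endpoint in a trial that says it will evaluate the difference in safety profiles (Protocol 2.0, SAP 1.1.3). With few infections the mean and SD may also be undefined or rest on a single patient.

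**Working it through.** **Denominator.** The plan raises 77 evaluable subjects per arm for 16% withdrawal: 77 / (1 - 0.16) = 91.7, rounded up to 92. This reproduces the stated 92. The 77 itself comes from the closure-time calculation and has no bearing on ASEPSIS. Neither document states an SSI rate or an expected number of ASEPSIS scores.

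**Direction of the conditional mean.** Suppose an arm has *m* mild infections scoring *a* and *v* severe ones scoring *b*. The planned mean is (*m*·*a* + *v*·*b*) / (*m* + *v*). It depends on the mix of mild and severe cases and not on how many subjects were infected, so the problem exists at any SSI rate.

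Illustration, with assumed counts and scores and 92 per arm. Control has three SSIs scoring 25 and one scoring 45. In the test arm the three milder infections are prevented and the one scoring 45 remains.

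| Summary | Control | Test |
|---|---|---|
| Planned mean among SSI cases | (3×25 + 45)/4 = 30.0 | 45/1 = 45.0 (SD undefined) |
| SSI incidence (already planned) | 4/92 = 4.3% | 1/92 = 1.1% |
| Mean over all subjects, no SSI counted as 0 | 120/92 = 1.30 | 45/92 = 0.49 |

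The planned mean favours control; the two summaries over all subjects favour the test arm. With the arms swapped, a closure that adds mild infections shows the lower mean.

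**Number of cases.** For SSI rate *p* and *n* = 92, the chance that a given arm has 0 or 1 case is (1 - *p*)^92 + 92·*p*·(1 - *p*)^91. The chance that at least one arm does, if both arms share the rate, is 1 minus the square of the complement. All rates are assumptions.

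| Assumed SSI rate | Expected cases per arm | P(0 or 1), given arm | P(0 or 1), at least one arm |
|---|---|---|---|
| 1% | 0.92 | 0.765 | 0.945 |
| 2% | 1.84 | 0.449 | 0.696 |
| 3% | 2.76 | 0.233 | 0.412 |
| 5% | 4.60 | 0.052 | 0.102 |
| 10% | 9.20 | 0.001 | 0.001 |

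A given arm is more likely than not to have 0 or 1 case only if the rate is below about 1.8%. For at least one arm, the threshold is about 2.7%. With 77 per arm these become about 2.2% and 3.2%.

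**The case against.** The strongest reply is that nothing turns on this table. No safety endpoint is tested, SAP 2.4 makes secondary endpoints supportive only, no interim analysis or data monitoring committee uses the score, and the primary analysis is untouched. ASEPSIS is defined as a measure of infection severity, so describing it among infected patients follows from its purpose. All of that stands and limits the size of the point. It does not make the two means comparable, and a by-arm table under an objective about differences in safety will be read as a comparison.

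A reader might infer that the plan hides how many infections each arm had. It does not: N is printed beside the mean, and SSI incidence on the Safety set is a planned summary. In the illustration that incidence shows the right direction.

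A reader might also infer that the mean will usually rest on no patient or one. The documents do not support this without an SSI rate. It is plausible at 1-2% and false at 5% or more. An undefined SD is in itself a display matter.

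Two further replies have some force. Adverse event listings, and the minimum and maximum when an arm has one or two cases, already reveal part of the individual data. The table and listing shells are in a separate document (SAP 7), so the absence of an ASEPSIS listing cannot be established; it can only be said that the SAP text specifies none. Finally, a replacement table limited to scores above 20, 30 and 40 would drop infections scoring 20 or less. The replacement therefore needs every category, including no SSI. It would still rest on the same few events.

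**Conclusion.** The concern holds in a limited form. The by-arm ASEPSIS mean conditions on an outcome that the closure method may change, so it is not a comparison of randomised groups and can run opposite to the wound outcome. This follows from the text and needs no outside figure. The 30 versus 45 in the illustration rests on assumed counts and scores; it shows that a reversal is possible, not that one is expected.

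The sparsity argument is secondary and conditional on the unstated SSI rate: 77% at 1%, 45% at 2%, 23% at 3% and 5% at 5% for a given arm of 92. The consequence is confined to the descriptive comparison of infection severity. The documents do not support a claim that the trial's safety conclusion as a whole would be wrong, since incidence of SSI, dehiscence and delayed healing are all reported on the Safety set. This is an improvement worth making, not a barrier to proceeding.

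**What to change.** In SAP 3.3, take ASEPSIS out of the continuous summaries. Report by arm the number and percentage of all Safety-set subjects in each row: no SSI; SSI with score 0-10; 11-20; 21-30; 31-40; above 40. Add a row for SSI with no score recorded, so that the SSI rows add up to the planned SSI incidence. In the illustration, control would show 88 (95.7%) with no SSI, 3 (3.3%) at 21-30 and 1 (1.1%) above 40; the test arm would show 91 (98.9%) with no SSI and 1 (1.1%) above 40.

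Before that:
- Reconcile the SAP's 20-30 band with the protocol's 21-30. As printed in the SAP, a score of 20 falls in two categories.
- State which score classifies a subject, since the schedule allows scoring at both Visit 4 and Visit 5.

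Add a listing of individual scores. If a mean is kept, label it as describing SSI cases and not as an arm comparison.

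The cost is one changed table shell and one listing, with no new data collection. The loss is a conventional mean and SD.
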